#### 4.8.3 Genitourinary Side Effects

Genitourinary side effects will include vaginal discharge, vaginal burning, vaginal itching, vaginal pain, and other vaginal symptoms as reported by the subject in her eDiary. Partner side effects (burning, itching, pain, and other side effects) will also be captured in eDiary. Number and percentage of subjects with genitourinary side effects and partner side effects will be summarized in the following stratifications:

- By the time of symptom onset after product application
  - < 5 minutes
  - 5 – 30 minutes

- 31 - 60 minutes
- > 1 hour
- By the severity of the symptom
  - Mild
  - Moderate
  - Severe
- By duration of the symptom
  - < 5 minutes
  - 5 – 30 minutes
  - 31 – 60 minutes
  - > 1 hour

#### 4.8.4 Gynecological Infections

The number and percentage of subjects responding to the question “Subject has a Vaginitis?” will be presented for the Safety Population by visit. The following types of vaginitis will also be summarized by visit for subjects responding Yes or No for Vaginitis:

- Yeast/Monilia
- Bacterial Vaginosis Trichomoniasis
- Other

Unscheduled visits will be grouped with associated visit (e.g., visit 3.1 will be included with visit 3).

#### 4.8.5 Dipstick Urinalysis and Urine Culture

Dipstick urinalysis analytes include blood (negative, trace, 1+, 2+, 3+), leukocyte esterase (negative, trace, 1+, 2+, 3+), protein (negative, trace, 1+), and nitrites (negative, trace, 1+, 2+, 3+,4+). Number and percent of subjects for each category will be presented by visit and final evaluation.

For urine culture and UTI results, number and percent of subjects will be presented for the Safety Population by visit and final evaluation. Urine culture result categories are as follows:  $\geq 100,000$  CFU/mL,  $< 100,000$  CFU/mL, indeterminate and negative. UTI result categories are as follows: Yes – a symptomatic UTI: compliant of urinary symptoms and 1+ for analytes of blood, leukocyte esterase, protein or nitrites and a minimum bacterial count of 10,000 colony forming units (CFU)/mL with the presence of uropathogen; Yes – a symptomatic UTI: presence of symptoms and  $\geq 100,000$  CFU/mL presence of uropathogen without a positive leukocyte esterase by dipstick; Yes – an asymptomatic UTI : absence of symptoms and a bacterial count of  $\geq 100,000$  CFU/mL with the presence of uropathogen; No – not per protocol definitions.

Wet mount assessment results are classified as normal or abnormal. The number and percentage of subjects with improved (changed from abnormal in baseline to normal), no change, and worsened (changed from normal in baseline to abnormal) results will be presented for each visit and final evaluation. Number and percent of subjects in each sub-category of abnormal wet

mount (including WBC, trichomonas, hyphae/spores, clue cells (>20%)) will also be presented. Vaginal pH will also be summarized for each visit and final evaluation.

Unscheduled visits will be grouped with the associated visit (e.g., visit 3.1 will be included with visit 3).

#### **4.8.6 Gynecological Examination**

For gynecological examinations, each body system will be categorized as normal or abnormal. Gynecological examination changes from baseline will be categorized as improved, no change, or worsened for each body system. The number and percentage of subjects in each category of change will be given at each visit and final evaluation and body system.

An adaptation of *the Division of AIDS (DAIDS) Table for Grading the Severity of Adult and Pediatric Adverse Events, Version 2.0, Addendum 1 – Female Genital Grading Table for Use in Microbicide Studies* will be used by the investigator to grade changes from baseline in vulvar, vaginal or cervical findings noted during the gynecologic exam and determine if they are considered significant, as defined as at least one grade increase from baseline (see appendix 5.1).

Vulvar, vaginal, and cervical findings will be summarized by visit and final evaluation. The number and percentage of subjects and events for each grade will be presented.

Unscheduled visits will be grouped with the associated visit (e.g., visit 3.1 will be included with visit 3).

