4.1.2 Exclusion Criteria

To enroll in the clinical study, potential subjects **must not**:

1. Have had three or more UTIs in the past year from the date of consent.

- 2. Have a UTI by urine culture, chlamydia, gonorrhea, or symptomatic yeast vaginitis or symptomatic BV diagnosed by wet mount, trichomoniasis, unless treated and proof of cure is documented within the screening period.
- 3. Have used vaginal or systemic antibiotics or antifungals within 14 days prior to enrollment, with the exception of vaginal or systemic antibiotics or antifungals completed for the treatment of a UTI, BV, or yeast vaginitis diagnosed at screening within seven days of the Enrollment Visit.
- 4. Have a history of any recurrent vaginal infections/disorders (either greater than or equal to four times in the past year or greater than or equal to three times in the previous six months from the date of consent).
- 5. Be pregnant, have a suspected pregnancy, or desire to become pregnant during the course of the study.
- 6. Have a history of diagnosed infertility or of conditions that may lead to infertility, without subsequent non-assisted reproductive technology intrauterine pregnancy.
- 7. Have any maternal contraindications to pregnancy (medical condition) or chronic use of medications for which significant evidence of fetal risk exists.
- 8. Have known or screen test-positive for HIV infection.
- 9. Have three or more outbreaks of genital HSV within the last year from the date of consent or be receiving suppressive therapy.
- 10. Have visible genital condylomata (warts).
- 11. Be lactating or breastfeeding.
- 12. Have any clinically significant abnormal finding on physical examination including pelvic examination or baseline laboratory assessments which in the opinion of the Investigator, precludes study participation.
- 13. Have clinically significant signs of vaginal or cervical irritation on pelvic examination.
- 14. Be planning to have any (e.g., diagnostic or therapeutic) vaginal or cervical procedures during the period of the study.
- 15. Have an abnormal Pap test based on the following criteria:
 - a. Pap test in the past 12 months from the date of screening with atypical squamous cells of undetermined significance (ASC-US) unless at least one of the following criteria is met:
 - i. Less than 21 years of age.
 - ii. A repeat Pap test at least six months later was normal.
 - iii. Reflex HPV testing was performed and was negative for high-risk HPV.

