- Review eDiary data report for completeness and accuracy, and assess the need for subject re-training in eDiary use
- Review study drug adherence data
- Review backup contraception use and sexual activity

- Collect unused study drug and unused applicators, and record study drug accountability information
- Re-supply study drug, as necessary
- Record concomitant medications (including any herbal or natural supplements)
- Record AEs
- Remind subjects of their right to use EC during the study
- Encourage subjects not to have intercourse, use the study drug, or place anything in the vagina within 24 hours of the next scheduled clinical site visit
- Visit 4 only: discuss post-study contraception with the subject to be started after completion of cycle 7 and before Visit 5/Exit Visit
- Schedule the next clinical site visit
- Confirm subject contact information

If the subject presents to an interim visit and is diagnosed with a UTI, symptomatic BV, trichomoniasis or symptomatic yeast vaginitis, she will be treated and allowed to continue in the study. All diagnosed or suspected conditions will be noted in the EDC system.

Based on gynecologic exam at each visit, investigators will note the presence or absence of vulvar, vaginal, or cervical findings (as defined in Section 5.4.3), including epithelial disruption, or areas of obvious erythema; these will be assessed as either not present, mild, moderate, or severe; the presence or absence of bleeding, petechiae, or sloughing will also be recorded on the gynecological exam eCRF. These findings will be reported as an AE if considered by the Investigator to be a clinically significant change from baseline, defined as an at least one level increase in severity of the finding from baseline.

If, during the eDiary review, the clinical site detects any pattern of incorrect or inconsistent drug usage, the subject will again be provided with proper usage instructions for the study drug. In addition, the eDiary data report will be reviewed to ensure that it does not contain reports of any signs or symptoms related to drug use. If a sign or symptom is reported in the subject eDiary that warrants follow-up, the subject may be contacted for further information as necessary and may be asked to return to the clinical site for evaluation and/or treatment.

At each interim visit, all subjects will be reminded to contact the clinical site as soon as possible if any of the following occur:

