An adaptation of the Division of AIDS (DAIDS) Table for Grading the Severity of Adult and Pediatric Adverse Events, Version 2.0, Addendum 1 – Female Genital Grading Table for Use in Microbicide Studies will be used by the investigator to grade changes from baseline in vulvar, vaginal or cervical findings noted during the gynecologic exam and determine if they are considered significant, as defined as at least one grade increase from baseline. These should be reported as AEs. The Female Genital Grading Table for Use in Microbicide Studies was developed for use in protocols involving topical application of products to the female genital tract. Although developed specifically for microbicide studies, it is applicable to other protocols as well to ensure data consistency across sites.

Parameter	Grade 0	Grade 1	Grade 2	Grade 3
	Normal	Mild	Moderate	Severe
Epithelial	None	Blisters,	Blisters,	Severe epithelial
disruption		ulcerations,	ulcerations, large	disruption with
		superficial	disruptions –	hospitalization
		disruptions with	treatment	indicated
		minimal impact	indicated	
		on life – no		
		treatment needed		
Erythema	None	Erythema	Erythema	Severe erythema
		covering <50%	covering ≥50%	with
		of surface	of surface	hospitalization
				indicated
Parameter	Grade 0	Grade 1		
Bleeding	None	Present		
Petechiae	None	Present		
Sloughing	None	Present		

Table 3: Vulvar, Vaginal, or Cervical Individual Signs/Symptoms Grading Table

Recording Adverse Events

AE reporting will extend from enrollment until Visit 5 (14-30 days after the seventh study cycle). AEs occurring after Visit 5 should be reported to PAREXEL by the Investigator if the Investigator considers there is a causal relationship with the study drug.

All AEs, regardless of the relationship to study drug, will be recorded in the EDC system.

All AE reports should contain a brief description of the event, date and time of onset, date and time of resolution, intensity, treatment required, relationship to study drug, action taken with the study drug, outcome, and whether the event is classified as serious.

AEs reported as ongoing at the last study visit will be listed as ongoing as of the last study date, and time of resolution will be marked as Not Applicable.

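### The planned change-from-baseline table for the gynecological examination rests on a normal/abnormal scale, and no planned table counts the women who meet the plan's own one-grade criterion

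*SAP*

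**What the plan says.** SAP 4.8.6 plans two summaries of the gynecological examination.

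- **Change by body system (Table 14.3.5.8).** The rule is that "each body system will be categorized as normal or abnormal. Gynecological examination changes from baseline will be categorized as improved, no change, or worsened". The section does not say how an organ that is abnormal at both baseline and a later visit is classed.
- **Graded findings (Table 14.3.5.9).** Vulvar, vaginal and cervical findings are graded with an adapted microbicide grading table (SAP Appendix 5.1; Protocol Table 3). Epithelial disruption and erythema run from Grade 0 to 3; bleeding, petechiae and sloughing are Grade 0 or 1. By visit and at final evaluation, "The number and percentage of subjects and events for each grade will be presented".

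The documents agree on what counts as an important change. Protocol 5.4.3 calls a change "significant, as defined as at least one grade increase from baseline", and SAP 4.8.6 repeats this. Protocol 5.1.3 (Visits 3 and 4) and 5.1.4 (Visit 5) express it as a clinically significant change, "defined as an at least one level increase in severity of the finding from baseline", to be reported as an adverse event.

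Only the wet mount paragraph of SAP 4.8.5 spells out the three change labels. There the third label reads "worsened (changed from normal in baseline to abnormal".

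At entry, exclusion 13 bars women who "Have clinically significant signs of vaginal or cervical irritation on pelvic examination". Lesser findings are not excluded.

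**The concern.** This is a single-arm trial of a vaginal product, so a woman's own baseline is the only internal reference for local findings. The examination is done at all five visits, and the grades are recorded each time. A change-from-baseline table built on two levels cannot show a worsening that stays within the abnormal level, yet such a worsening can meet the plan's own definition of a significant change.

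At stake is one descriptive result under the secondary safety objective. A reader of Table 14.3.5.8 would take *no change* to mean stable when it can include women who worsened, or improved, by one or more grades. Elsewhere the SAP does show within-woman shifts: 4.8.8 plans baseline-to-final shift tables for hematology and chemistry (Tables 14.3.5.12 and 14.3.5.14). It plans none for the graded local findings.

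**Working it through.** The plan gives no figure to reproduce. The check is which grade changes a two-level scale can register.

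**Assumptions.** The body systems are the organs examined under the protocol (vulva, vaginal wall, cervix, adnexae, uterus). Grade 0 is normal and Grade 1 or more is abnormal. *Worsened* means normal to abnormal, as for wet mount in SAP 4.8.5. SAP 4.8.6 states none of these.

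**Step 1: one parameter graded 0 to 3.** Four grades give 4 × 3 / 2 = 6 upward transitions.

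| Transition | Normal/abnormal scale | One-grade criterion |
|---|---|---|
| 0 to 1, 0 to 2, 0 to 3 | worsened | met |
| 1 to 2, 1 to 3, 2 to 3 | no change | met |

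Three of the six are registered and three are not. By symmetry, three of the six downward transitions (2 to 1, 3 to 1, 3 to 2) are hidden too.

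**Step 2: does another cut-off help?** If mild findings were recorded as normal (cut between 1 and 2), four upward transitions register, but 0 to 1 and 2 to 3 do not. With a cut between 2 and 3, three register, and 0 to 1, 0 to 2 and 1 to 2 do not. No single cut captures all six, so no two-level scale can reproduce the one-grade criterion.

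**Step 3: several parameters in one organ.** Taken singly, bleeding, petechiae and sloughing lose nothing on a two-level scale. The table, however, classifies the organ. If the cervix has mild erythema at baseline and an epithelial disruption or petechiae appears later, the cervix is abnormal both times, although one parameter has gone from 0 to at least 1.

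**Step 4: who can be affected.** Only women whose organ is already abnormal at baseline, under the Step 1 mapping. Exclusion 13 removes clinically significant vaginal or cervical irritation, so this group exists but is restricted. Neither document gives its size.

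**Step 5: do other planned outputs supply the count?**

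- *Table 14.3.5.9* counts subjects and events per grade by visit, with no stated link to the same woman's baseline grade. Comparing counts between visits is not a substitute, because different women contribute. The sample size sections assume drop-out of 10% in month 1 and 38% in months 2 to 6, with 515 completers expected of 1349 (515 / 1349 = 38%). The final-evaluation summary is less exposed, since women who stop early are asked to have the exit examination (Protocol 6.4), but it still shows marginal counts rather than shifts.
- *Adverse event tables* (SAP 4.8.2) are by system organ class and preferred term, with intensity on CTCAE grades (Protocol 5.4.3) rather than the genital grading table. Protocol Table 1, footnote g, also leaves clinical significance to the investigator's judgement. A one-grade increase reported as an event is included but cannot be identified as such.
- *Listings* 16.2.9.1 and 16.2.7.1 cover the examination and adverse events by subject, but they are not summaries.

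No planned table gives the number or percentage of women with at least a one-grade increase.

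**The case against.** The strongest reply is that little is lost. SAP 4.8.6 does not say that abnormal-to-abnormal is *no change*; that is carried over from the wet mount rule. The graded summary sits in the same section, so a rise from mild to moderate or severe would appear there as a higher-grade count. The one-grade criterion already has a use: under the protocol it triggers adverse event reporting, and those events are tabulated. Neither document requires Table 14.3.5.8 to apply that threshold, so a coarser descriptive scale there does not contradict the plan.

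Much of this stands. A reader might infer that the SAP expressly scores mild-to-severe as unchanged, or that such worsening disappears from the safety output. The documents support neither: the mapping is unstated, and the grade counts and adverse event tables carry part of the information. A reader might also infer that Table 14.3.5.9 certainly mixes pre-existing with new findings. That is open too, because the text says the grading table is used to grade changes from baseline and then counts findings per grade without saying which are included.

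The limitation of the two-level scale survives, since it holds for any cut-off. So does the missing count. If some other mapping was intended, SAP 4.8.6 needs to state it.

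**Conclusion.** The point holds as a minor gap in safety presentation. SAP 4.8.6 leaves *improved*, *no change* and *worsened* undefined for the gynecological examination. On the natural reading, Table 14.3.5.8 would show as unchanged some women who meet the plan's own one-grade criterion, and no other planned table counts them.

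Two further inferences should be avoided. The first is that the error runs only towards under-reporting harm. The *worsened* count can only be too low under this mapping, but decreases within the abnormal range are hidden as well, so the table is blunt in both directions. The second is a headcount. If 5% of 1349 women worsened (1349 × 0.05 = 67), 5% to 20% had an abnormal organ at baseline, and worsening were independent of baseline status, about 3 to 13 women would be misclassified (67.45 × 0.05 = 3.4; 67.45 × 0.20 = 13.5). Neither rate stands in the documents, and 1349 is the planned enrolment rather than the Safety Population, so this only illustrates scale. The true number cannot be stated, and exclusion 13 probably keeps it small.

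The conclusion rests on the Step 1 assumptions; Step 2 shows that the choice of cut-off does not change it. The primary analysis and clinical management are unaffected.

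**What to change.** In SAP 4.8.6:

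1. For vulva, vagina and cervix, define change by the recorded grades. *Worsened*: at least a one-grade increase from baseline in any of the five graded parameters, including one that is newly present. *Improved*: at least a one-grade decrease in one or more parameters with no increase in any. *No change*: otherwise.
2. Keep normal/abnormal for adnexae and uterus, which have no grading, and state there how abnormal at both times is classed.
3. Add to Table 14.3.5.9 a shift of worst post-baseline grade against baseline grade for each parameter, with the number and percentage of women who have at least a one-grade increase at any time.

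The cost is a few lines of SAP text and one extra table panel. The grades are already recorded on the gynecological examination eCRF, so no new data are needed. The reported percentage worsened may become slightly less favourable.

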#### **4.8.7 Sexually Transmitted Infection Tests**

Sexually transmitted infections (STI) tests for chlamydia and gonorrhea will be classified as positive or negative. The number and percentage of subjects in each test result will be presented by visit. Unscheduled visits will be grouped with the associated visit (e.g., visit 3.1 will be included with visit 3).

#### **4.8.8 Clinical Laboratory Evaluation**

CBC and chemistry and their change from baseline to final evaluation will be summarized.

A summary of shifts from baseline to final evaluation will be given for each parameter. The normal range for each parameter will be used to create categories of low, normal, or high. Any result that is higher (lower) than the upper (lower) limit of normal will be categorized as high (low) and any result within the lower and upper limits of normal will be categorized as normal.

CBC and chemistry data will be located in separate tables.

#### **4.8.9 Vital Signs**

Vital signs and weight and their change from baseline will be summarized by visit. Unscheduled visits will be grouped with the associated visit (e.g., visit 3.1 will be included with visit 3).

#### **4.8.10 Pregnancy Outcome**

The pregnancy outcomes will be summarized as follows:

- The number and percentages for each fetal status category (pre-term birth, full term birth, stillbirth, spontaneous termination, induced termination, ectopic pregnancy, unknown).

- The number and percentages for sex of fetus (male, female, unknown)
- The number and percentages for maternal complications
- Summary statistics (sample size, mean, median, SD, minimum, and maximum) for Apgar Scores (1 min and 5 min)
- Summary statistics (sample size, mean, median, SD, minimum, and maximum) for the gestational age (weeks)
- Summary statistics (sample size, mean, median, SD, minimum, and maximum) for the birth weight (pounds)

## 4.9 Subject Satisfaction

All analyses described in this section will be performed on the Safety population.

### 4.9.1 Subject Satisfaction Questionnaires

Four endpoints will be defined for Subject Satisfaction Questionnaires:

- Satisfaction level to study product which will be evaluated at baseline and visit 3-5 based on the answers to question “how satisfied were you with your most recent/study birth control method”:
  - a. Very satisfied
  - b. Satisfied
  - c. Somewhat satisfied
  - d. Somewhat dissatisfied
  - e. Dissatisfied
- Likelihood of recommendation as a vaginal contraceptive gel which will be evaluated at Visit 3-5 with outcome:
  - f. Very likely
  - g. Likely
  - h. Somewhat likely
  - i. Somewhat unlikely
  - j. Unlikely
- Likelihood of recommendation as another birth control option which will be evaluated at Visit 3-5 with outcome:
  - k. Very likely
  - l. Likely
  - m. Somewhat likely
  - n. Somewhat unlikely
  - o. Unlikely
- Likelihood to continue use which will be evaluated at Visit 3-5 with outcome:
  - p. Very likely

- q. Likely
- r. Somewhat likely
- s. Somewhat unlikely
- t. Unlikely

All four endpoints will be summarized using frequency and percentage by visit and outcome level. Unscheduled visits will be grouped with the associated visit (e.g., visit 3.1 will be included with visit 3).

#### 4.9.2 Sexual Function Questionnaire

The Sexual Function Questionnaire has 10 variables:

1. Vaginal dryness during sexual activity
2. Lack of sexual interest or desire
3. Vaginal tightness
4. Pain during penetration or intercourse
5. Anxiety about your sexual performance
6. Unable to orgasm
7. Vaginal bleeding or irritation from penetration or intercourse
8. Increased sensitivity of your skin to intimate touching
9. Sharp pain inside or outside your vagina
10. Other problem with sexuality

The outcomes and coding for these 10 Variables are provided in Table 3.

